6.1.2 Secondary Endpoints

- **Common grade ≥ 2 toxicities** from cisplatin + doxorubicin (other than cisplatin nephrotoxicity and ototoxicity), including myelosuppression, mucositis, nausea and vomiting leading to dehydration requiring IV fluid hydration, peripheral neuropathy, cardiac dysfunction, and treatment delays due to toxicity will be collected and graded according to CTCAE v.4. Similarly, HDMTX-related grade ≥ 2 toxicities (other than nephrotoxicity), including myelosuppression, mucositis, dermatitis, hepatotoxicity and neurotoxicity will be collected and graded. The incidence and severity (grade) of toxicities will be tabulated and compared by treatment arm (with vs. without

pantoprazole for cisplatin + doxorubicin and by infusion duration for HDMTX).

- **Response** to 2 cycles of neoadjuvant chemotherapy will be assessed radiographically and histologically.
 - The volume of the tumor on MRI will be measured pretreatment and pre-operatively (post-cycle 2). The log ratio (Section 5.2) of the two measurements will be derived and compared using a non-parametric analysis for cisplatin with (patients on treatment arms 1 and 3) vs. without (patients on treatment arms 2 and 4) pantoprazole and for HDMTX administered as a 4 h infusion (treatment arms 1 and 2) vs. a 12 h infusion (treatment arms 3 and 4).
 - The tumor specimen that is removed after 2 cycles of neoadjuvant chemotherapy will be evaluated histologically and the percent of the tumor that is necrotic will be estimated from review of multiple sections. The percent necrosis will be compared using a non-parametric analysis for cisplatin with (patients on treatment arms 1 and 3) vs. without (patients on treatment arms 2 and 4) pantoprazole and for HDMTX administered as a 4 h infusion (treatment arms 1 and 2) vs. a 12 h infusion (treatment arms 3 and 4).
- **GFR** estimated from serum creatinine using the modified Schwartz formula will be correlated with GFR estimated from serum cystatin C (Section 1.3.3, the equation also includes serum creatinine and BUN). The presence and amount (normalized to creatinine concentration) of biomarkers of AKI in urine will be correlated with proteinuria, serum creatinine, and change in FEMg.
- **BSAP** levels will be correlated with tumor volume and presence or absence of metastatic disease at diagnosis. BSAP after 2 cycles of neoadjuvant chemotherapy will be correlated with tumor volume and percent tumor necrosis post-cycle 2. BSAP drawn post-operatively, at the end of therapy and at the time of relapse will be correlated with disease status.
- An osteosarcoma-specific **Patient Reported Outcome survey** will be used to assess disease-related and treatment-related symptoms and tested in the patients enrolled on this trial. The patient reported outcomes will be compared to toxicity data collected from the medical record and to physician assessments of patient status (performance score).

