3.1.3 Treatment with MAP Regimen

All patients will receive 6 cycles of the 3-drug MAP chemotherapy regimen (Methotrexate, Adriamycin [doxorubicin] and cisPlatin) that is shown in Figure 2. Cycles 1 & 2 will be administered neoadjuvantly (before resection of the primary tumor). After recovery from surgery, patients will resume treatment with 2 cycles of MAP followed by 2 cycles of MA (no cisplatin).

Treatment arm specific treatment delivery maps (TDM) will be generated for each patient after randomization and placed in the clinic chart to serve as a guide. Appendix 1 shows an example of a TDM.

Standard treatments: Cycles 1-4 of MAP are 5 weeks (35 days) in duration. Cisplatin and doxorubicin are administered on days 1 & 2 and HDMTX + leucovorin rescue is infused on days 22 & 29. cisplatin is not administered in Cycles 5 & 6 and the duration of Cycles 5 & 6 is 4 weeks (28 days). During cycles 5 & 6, doxorubicin is administered on days 1 & 2 and HDMTX + leucovorin rescue is infused on days 15 & 22. Supportive care/rescue agents that are administered with MAP to alleviate toxicity include antiemetics (see CHOP Cancer Center

Protocol number: CHP12ST051
Amendment number:
Version date: April 2, 2013

antiemetic guidelines), dexrazoxane as a cardioprotectant, pegfilgrastim to facilitate neutrophil recovery after doxorubicin, and leucovorin as a HDMTX rescue agent. Intravenous fluid hydration is administered with cisplatin and HDMTX to prevent nephrotoxicity, and urine alkalinization is used to increase the solubility of MTX in urine.

Research Interventions: Pantoprazole will be administered intravenously with cisplatin on 2 consecutive treatment cycles (either Cycles 1 & 2 or Cycles 3 & 4), and the order of pantoprazole administration will be determined by randomization (see Study Diagram). Patients will receive HDMTX as 4 and 12 h infusions on 2 consecutive treatment cycles (Cycles 1 & 2 or Cycles 3 & 4), and the order of the infusion durations will be determined by randomization.

Drug doses, schedules, and administration routes: for the chemotherapy and supportive care/rescue medications are listed below:

- **Dexrazoxane** 375 mg/m²/dose IV over 15 min immediately prior to the doxorubicin doses on days 1 & 2 (total dose 750 mg/m²/cycle) of treatment cycles 1-6;
- **DOXOrubicin** 37.5 mg/m²/dose IV over 15 min on days 1 & 2 (total dose 75 mg/m²/cycle) of treatment cycles 1-6 (total cumulative dose 450 mg/m²);

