3.4 Study Population

3.4.1 Study Enrollment/Registration

Subjects are enrolled on study after fulfilling the eligibility criteria listed below. Treatment arm will be assigned by the Study PI based on a spreadsheet provided by the Study Biostatistician. Demographic information, results of screening and baseline studies, tumor site(s) and histology, and treatment arm will be entered into OnCore CRM. **Patients must be enrolled and randomized prior to starting neoadjuvant chemotherapy.**

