6.1 Statistical Analysis Plan

6.1.1 Primary Endpoints

- **Urinary KIM-1, NAG and NGAL** will be normalized to the urinary creatinine concentration measured in the same urine specimen and expressed as ng/mg Cr. The end of infusion and 7-day post values for each biomarker will be analyzed by course for cisplatin with vs. without pantoprazole and by dose for HDMTX administered as a 4 h vs. 12 h infusion.
- **GFR** will be estimated from serum creatinine and from the cystatin C (see Section 1.3.3) prior to each course of cisplatin and each dose of HDMTX and 7-days post treatment. A decrease in the GFR will reflect toxicity from the immediately preceding course of

Protocol number: CHP12ST051
Amendment number:
Version date: April 2, 2013

cisplatin or dose of HDMTX. Change in GFR will be analyzed by course for cisplatin with vs. without pantoprazole and by dose for HDMTX administered as a 4 h vs. 12 h infusion.

- Change in **FEMg** from pre-dose 1 (day 1 of cycles 1-4) of cisplatin to pre-dose 2 (day 2 of cycles 1-4) of cisplatin and day 7 will be measured for each cycle containing cisplatin (n=4). Change in FEMg will be analyzed by course for cisplatin with vs. without pantoprazole to assess renal tubular toxicity.
- The **urinary MTX concentration** at the end of each HDMTX infusion on cycles 1-4 will be tabulated for the 4 and 12 h infusion durations and compared to the MTX solubility limit for the urine pH to determine whether the solubility limit was exceeded. End infusion urine MTX concentration will also be correlated with simultaneous serum concentration and with the severity of renal toxicity as measured by AKI biomarkers and serum creatinine and serum cystatin C.
- An **audiogram** will be performed prior to Cycles 1, 2, 3 and 4 and at the end of therapy (after cycle 6). The average hearing level (HL) threshold in dB over the frequency range of 4,000-8,000 Hz will be derived separately for each ear from each audiogram. The increase in the average HL threshold in dB from the pre-cycle 1 to pre-cycle 2, from pre-cycle 2 to pre-cycle 3, from pre-cycle 3 to pre-cycle 4, and from pre-cycle 4 to end of therapy audiograms will be derived and this increase in HL threshold will be compared for cisplatin with vs. without pantoprazole.

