6.3 Interim Analysis

The sample size in this pilot study is too small to derive a statistically valid stopping rule with sufficient sensitivity. However, after the first 12 patients have completed treatment, the investigators will evaluate the following parameters to determine whether pantoprazole or prolonging the HDMTX infusion affect toxicity or anti-tumor response to MAP:

- The incidence and severity (CTCAE grade) of toxicities will be compared for

Protocol number: CHP12ST051
Amendment number:
Version date: April 2, 2013

cisplatin/doxorubicin with vs. without pantoprazole and for HDMTX infused over 4 h vs. 12 h within and across patients.

- Radiographic response (log ratio) and histological response (% tumor necrosis) following 2 cycles of neoadjuvant chemotherapy will be compared in patients who received pantoprazole vs. patients who did not receive pantoprazole and in patients who received HDMTX over 4 h vs. 12 h.

If the toxicity from MAP is clinically significantly worse when cisplatin is administered with pantoprazole or when HDMTX is infused over 12 h OR if radiographic or histological response to neoadjuvant chemotherapy is clinically significantly less in patients receiving pantoprazole or a prolonged HDMTX infusion, then the intervention found to have the worse outcome will be discontinued.

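### No masked reading is specified for percent necrosis, MRI tumour volume or audiograms, although the arm is filed in the clinic chart and the two response measures can end an intervention

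*Combined protocol and SAP*

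**What the plan says.** **How the reads are made.** Section 6.1.2 says of the resected specimen that "the percent of the tumor that is necrotic will be estimated from review of multiple sections". It has MRI tumour volume measured before treatment and again before surgery. For hearing, Section 6.1.1 says: "The average hearing level (HL) threshold in dB over the frequency range of 4,000-8,000 Hz will be derived separately for each ear from each audiogram". None of these sections says who does the reading or what that person may know about treatment.

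**Where the arm is visible.** Section 3.1.3 says: "Treatment arm specific treatment delivery maps (TDM) will be generated for each patient after randomization and placed in the clinic chart". Section 3.4.1 says: "Treatment arm will be assigned by the Study PI based on a spreadsheet provided by the Study Biostatistician". The protocol mentions no placebo, blinding, or masked or central reading for any endpoint.

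**What the reads decide.** In Section 6.3 the investigators compare toxicity, radiographic response and histological response once 12 patients have finished treatment. If they judge toxicity worse, or response less, by a clinically significant amount, "then the intervention found to have the worse outcome will be discontinued". No numeric limit is given; the section explains that the sample is too small for a valid statistical stopping rule. Section 5.4 also puts the ototoxicity endpoints into a 12-patient review, but Section 6.3 does not list audiograms.

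**The concern.** Most of the primary endpoints are laboratory assays, where knowing the arm matters little. Necrosis, tumour volume and audiometric thresholds are different, because a reader who expects one arm to do better can lean without noticing.

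For the two response measures the crossover gives no protection. Response is assessed once, after Cycles 1 and 2, so arms 1 and 3 are compared with arms 2 and 4 for pantoprazole, and arms 1 and 2 with arms 3 and 4 for infusion duration. A lean linked to the arm goes straight into that contrast. The contrast then goes to investigators who know the arms and have no numeric limit. Neither the read nor the decision has a safeguard against expectation.

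Two errors are possible: dropping an intervention that does no harm, or continuing one that weakens the anti-tumour effect. The second is the more serious.

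Hearing is a separate matter. It is a primary endpoint (Section 5.1), so the stake there is the final comparison with and without pantoprazole.

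**Working it through.** **Inputs**
- Section 3.2: 3 of the first 12 patients in each of 4 arms; 6 per arm at full enrolment.
- Section 6.2: between-patient comparison of 12 against 12, 80% power, two-sided 5% level, detectable difference 1.2 SD. This figure is given for hearing, but response is also compared between patients.
- Assumed, because the documents give neither: a reader lean b of 0, 0.25 or 0.5 SD, and an observed deficit of 0.5 SD as the point at which investigators would act.

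**Step 1. The plan's own figure.** For a two-sample t test with n per group, the noncentrality is d/√(2/n). With d = 1.2 and n = 12 this is 1.2/0.408 = 2.94 on 22 degrees of freedom. Power is 80.2%, and the difference detectable with 80% power is 1.197 SD. The stated 1.2 SD reproduces.

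**Step 2. Size of the interim response comparison.** 3 per arm × 2 arms = 6 per level of each factor. It is *about* 6 against 6 because the first 12 to finish need not be the first 12 randomized. The same calculation with n = 6 (10 degrees of freedom) gives a detectable difference of 1.80 SD. The t test stands in here for the planned non-parametric test. The interim look can reveal only very large differences reliably, so the decision rests on judgement.

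**Step 3. What a lean would do to that judgement.** In SD units the standard error of the difference is √(2/n): 0.577 for n = 6 and 0.408 for n = 12.

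With no true effect and a lean b against the intervention, P(looks worse by at least 0.5 SD) = Φ((b − 0.5)/SE):

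| Lean b | 6 vs 6 | 12 vs 12 |
|---|---|---|
| 0 | Φ(−0.866) = 19% | Φ(−1.225) = 11% |
| 0.25 SD | Φ(−0.433) = 33% | Φ(−0.612) = 27% |
| 0.5 SD | Φ(0) = 50% | Φ(0) = 50% |

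With a true loss of 1 SD and a lean b in favour, at 6 vs 6, P(looks worse by at least 0.5 SD) = Φ((1 − b − 0.5)/SE):

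- b = 0: Φ(0.866) = 81%
- b = 0.25 SD: Φ(0.433) = 67%
- b = 0.5 SD: Φ(0) = 50%

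**Step 4. Hearing.** The analysis uses increments between successive audiograms. Suppose every audiogram that follows a pantoprazole cycle is read δ too low (too good), and the others are read correctly.

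- Pantoprazole first: the errors in the four increments are −δ, 0, +δ, 0. The pantoprazole mean is −δ/2 and the control mean +δ/2, a difference of −δ.
- Pantoprazole second: the errors are 0, 0, −δ, 0. The pantoprazole mean is −δ/2 and the control mean 0, a difference of −δ/2.
- Averaged over the two orders: (−δ − δ/2)/2 = −0.75δ.

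Differencing removes the error within a block after its first increment, but the treatment contrast keeps three quarters of it. The size of δ is unknown.

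**The case against.** The strongest reply is that the documents do not show any reader seeing the arm. The treatment map is a guide to drug delivery, and nothing says that a pathologist, radiologist or audiologist opens it. This is correct. What can be said is that the plan does not mask the readers and that the arm is in the chart.

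A reader might also infer that a biased audiogram could stop an intervention. The documents do not support that directly. Section 6.3 names the two response measures and graded toxicities, and Section 6.1.2 leaves ototoxicity out of the common-toxicity comparison. Hearing reaches the 12-patient review only through Section 5.4.

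A third tempting reading is that bias would run towards a wrongful stop. The protocol's own argument is that neither intervention should weaken the anti-tumour effect (Sections 1.3.2 and 1.3.5). A reader who shares that view would more likely hide a loss than invent one. The direction is open.

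It can also be said that this is a signal-finding pilot, that response is secondary, and that masked reads leave the investigators' own judgement unmasked. These points limit the weight of the concern. They do not remove it, because the response reads feed a decision with real consequences and hearing is primary.

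Finally, audiograms, MRI and necrosis are standard-of-care procedures, and Section 3.1.1 allows baseline tests before consent. This restricts how masking can be done, but tests done before randomization are free of the arm by their timing.

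**Conclusion.** The gap is real and worth closing. The plan does not mask whoever reads necrosis, MRI volume or audiograms; the arm is filed in the chart; and the two response measures enter a between-patient comparison of about 6 against 6 that can end an intervention on judgement alone. Expectation could create or hide a loss of response. The hearing comparison is exposed in its final analysis, and the crossover does not remove a lean that follows pantoprazole status.

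The documents do not establish that any read is biased, in which direction, or by how much. The percentages for response rest on assumed leans of 0 to 0.5 SD and an assumed 0.5 SD trigger, and they use a normal approximation. They show how sensitive the decision is and do not predict an outcome. No stated sample-size or power figure is in dispute.

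**What to change.** State in Sections 5.2, 6.1.1 and 6.1.2 that the existing pathologist, MRI volume reader and audiologist record every post-randomization read without being told the arm, the pantoprazole status or the HDMTX infusion duration, and without consulting the treatment delivery map until the read is signed. Routine clinical requests keep their usual identifiers and omit arm information. Pre-randomization baseline reads need no change, and signed results go to the treating team as usual.

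State that these reads are the ones used in the Section 6.3 comparison and in the final analysis. Sections 5.4 and 6.3 should also be reconciled on whether hearing is part of the 12-patient decision.

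The cost is wording and discipline about chart access. No readers or tests are added, and N, alpha and power stay as they are. Masking will be imperfect: staff can open the chart, and with no placebo patients can know their treatment, which matters most for a behavioural hearing test. The investigators' interim judgement also remains unmasked.

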STUDY DESIGN	
A randomized cross-over, 2 x 2 factorial design, in which patients serve as their own control, will be used to maximize the potential to detect differences in biomarkers of AKI (NAG, NGAL, KIM-1, cystatin C) and audiograms resulting from altering the infusion duration of HDMTX and from adding pantoprazole to cisplatin.
 
Two infusion durations of HDMTX will be studied – the standard 4 h duration and more prolonged 12 h infusion duration. Leucovorin rescue will commence 24 h from the start of the infusion. The HDMTX infusions will be divided into 2 blocks (cycles 1 & 2, cycles 3 & 4), each of which include 4 HDMTX infusions. The order of infusion duration studied in each block will be randomly determined.
 
Pantoprazole will either be administered with the first two courses of cisplatin during cycles 1 & 2 or with the third and fourth courses during cycles 3 & 4, and the order will be assigned by randomization. Cisplatin is administered as a 60 mg/m² dose infused over 4 h daily x 2 d. At steady state, 7.2 mg/m² of active cisplatin is in the body, and by the end of the 4 h infusion, 88% of the total dose has been cleared. Therefore, adequate concentrations to inhibit OCT2 should be present for at least 4 h to prevent cisplatin nephrotoxicity and ototoxicity. Pantoprazole has a short half-life (1.2 h), and when administered at a dose of 1.6 mg/kg as a standard 15 min infusion, plasma pantoprazole concentration by the end of the 4 h cisplatin infusion is 1.3 mcM. By administering the same dose as a 0.3 mg/kg loading dose infused over 15 min followed by a 4 h infusion of the remaining 1.3 mg/kg, plasma pantoprazole concentration is 5.9 mcM at 4 h.
 
The primary endpoint to assess nephrotoxicity will be the AKI markers (cystatin C, KIM-1, NGAL, NAG) and fractional excretion of magnesium (FEMg). This will allow us to assess each course of HDMTX and cisplatin independently. Standard renal function tests (urinalysis, serum creatinine, estimated creatinine clearance, and FEMg) will also be monitored. Audiograms will be performed after each course of cisplatin to assess ototoxicity. Radiographic and histological response in the resected tumor specimen after neoadjuvant chemotherapy will be assessed to ensure that changes in HDMTX infusion duration and the addition of pantoprazole to cisplatin do not alter the efficacy of chemotherapy.
 
A brief survey to assess the patient’s view of disease-related and drug toxicity-related symptoms will be piloted prior to each treatment cycle, post-op and at the end of therapy, and nutritional status will be monitored over the course of therapy.
 
The use of:
 
 • sensitive, short-term biomarkers as endpoints to assess the effect of interventions, • continuous, rather than categorical, variables that are analyzed by course or cycle rather than by patient, and • a crossover design with patients serving as their own control, 
will minimize the number of subjects and time required to complete this pilot study in a limited patient population with a rare form of cancer, increase statistical power, and

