SAFETY EVALUATION	
Nadir neutrophil count and duration of severe (ANC <500/mcL) neutropenia, nadir platelet count and number of platelet transfusions, hospital admissions/days for neutropenia with fever or infection, highest value for serum ALT and total bilirubin, grade 3 or 4 mucositis, treatment delays or missed chemotherapy doses to allow for recovery from toxicity, dose modifications for toxicity, and deaths attributed to chemotherapy toxicity will be monitored and collected by cycle.
 
After the first 12 patients have completed therapy, the incidence and severity of the events listed above as well as the nephrotoxicity and ototoxicity endpoints will be assessed by Cycle according to HDMTX infusion duration (4 h vs. 12 h) and according to whether or not IV pantoprazole was administered with cisplatin to ensure that the experimental dosing methods are not associated with excessive toxicity.
 
After the first 12 patients have undergone resection of their primary tumor, the radiographic response (log ratio) and histologic response (% necrosis) will be assessed according to HDMTX infusion duration (4 h vs. 12 h) during Cycles 1 & 2 and according to whether or not IV pantoprazole was administered with cisplatin during Cycles 1 & 2 to ensure that the anti-tumor effect of the MAP chemotherapy regimen is not compromised by the experimental dosing methods.

Protocol number: CHP12ST051

Amendment number:

Version date: April 2,, 2013

STATISTICAL AND ANALYTIC PLAN	
This pilot study uses a 2 x 2 factorial, randomized crossover design, which will allow patients to serve as their own control. Nephrotoxicity data will be analyzed by course for cisplatin and by dose for HDMTX, and ototoxicity data will be analyzed by cycle.
 
The primary endpoints are sensitive urinary biomarkers of AKI, standard renal function tests, and audiograms, and all endpoints will be analyzed as continuous variables.
 
Twenty-four patients will be enrolled and patients serve as their own control. Over the past 5 years, 57 newly diagnosed patients with osteosarcoma were seen and treated at CHOP. This is an average of 11.5 patients per year, indicating that we can complete accrual to this study in about two years. For each primary endpoint, separate linear mixed effects models will be constructed for comparison of cisplatin with vs. without pantoprazole and for comparison of the 4 vs. 12 h infusion durations of HDMTX.

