Cisplatin is administered as a 60 mg/m² dose infused over 4 h daily x 2 d, and Figure 9 is a PK simulation showing the amount of active drug in the body (assuming a half-life of 20 min) and the percent of the total dose cleared. At steady state, 7.2 mg/m² of active cisplatin is in the body, and by the end of the 4 h infusion, 88% of the total dose has been cleared. Therefore, adequate concentrations to inhibit OCT2 should be present for at least 4 h to prevent cisplatin nephrotoxicity and ototoxicity. Pantoprazole has a short half-life (1.2 h),³ and when administered at a dose of 1.6 mg/kg as a standard 15 min infusion (Figure 10), plasma pantoprazole concentration by the end of the 4 h cisplatin infusion is 1.3 mcM. By administering the same dose as a 0.3 mg/kg loading dose infused over 15 min followed by a 4 h infusion of the remaining 1.3 mg/kg, plasma pantoprazole concentration is 5.9 mcM at 4 h (Figure 10).

The primary endpoint to assess nephrotoxicity will be the AKI biomarkers (cystatin C, KIM-1, NGAL, NAG) described in Section 1.3.3. This will allow us to assess each dose of HDMTX and each course of cisplatin independently. Standard renal function tests (urinalysis, serum creatinine, creatinine clearance, and fractional excretion of magnesium) will also be monitored. Audiograms will be performed after each course of cisplatin to assess ototoxicity. Radiographic response and histological response in the resected tumor specimen after neoadjuvant chemotherapy will be assessed to ensure changes in HDMTX infusion duration and the addition of pantoprazole to cisplatin do not alter the efficacy of chemotherapy. The toxicity of the regimen will be closely monitored, and we will pilot a disease-specific patient reported outcome survey to assess the impact of tumor-related and drug toxicity-related symptoms.

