3.2 Randomization

Patients will be randomized to one of 4 treatment arms (see Study Diagram), which will determine the order in which they receive pantoprazole with cisplatin (Cycles 1&2 vs. Cycles 3&4) and the order in which they will receive HDMTX as a 4 or 12 h infusion (Cycles 1&2 vs. Cycles 3&4). A block randomization procedure will be used so that 3 of the first 12 subjects will be randomly assigned to each of the 4 treatment arms (three patient per arm) and 3 of subjects 13 to 24 will be randomly assigned to each of the 4 arms (six patients per arm when enrollment is completed). Subjects who are unable to complete 4 cycles of therapy may be replaced, and the new subject will be placed on the same treatment arm as the subject being replaced.

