3.3.2 Number of Subjects and Number of Study Sites

This pilot study will be conducted at CHOP. We plan to study 24 subjects. Patients who do not complete 4 cycles of treatment for any reason may be replaced. We may enroll up to 28 subjects in order to have 24 fully evaluable subjects. Based on the number of children with OS seen at CHOP annually, we expect accrual to be complete in 2 to 3 years.

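### Tumour response is assessed to ensure that efficacy is unaltered, but a between-patient comparison of about 12 versus 12 with no interval estimate can only screen for a large loss

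*Combined protocol and SAP*

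**What the plan says.** **Purpose.** The Synopsis (Study Design) says that response in the resected specimen and on imaging "will be assessed to ensure that changes in HDMTX infusion duration and the addition of pantoprazole to cisplatin do not alter the efficacy of chemotherapy". Section 1.3.7 says nearly the same. The Synopsis (Safety Evaluation) and Section 5.4 describe a separate look at response after the first 12 resections, "to ensure that the anti-tumor effect of the MAP chemotherapy regimen is not compromised by the experimental dosing methods".

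**Analysis.** Section 6.1.2 gives one method for both response measures. For necrosis: "The percent necrosis will be compared using a non-parametric analysis for cisplatin with" pantoprazole versus without. The groups are "patients on treatment arms 1 and 3) vs. without (patients on treatment arms 2 and 4) pantoprazole" and, for methotrexate, "a 4 h infusion (treatment arms 1 and 2) vs. a 12 h infusion (treatment arms 3 and 4". The log ratio of tumour volumes is handled the same way. The section names no specific test, alpha, sidedness, margin or confidence interval.

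**Numbers.** Section 3.2 gives "six patients per arm when enrollment is completed", and Section 3.3.2 adds "We may enroll up to 28 subjects in order to have 24 fully evaluable subjects". Section 6.2 states detectable differences for the kidney biomarkers, the HDMTX comparison and hearing, but none for response.

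**The concern.** The stated purpose and the planned analysis do not match. Assurance that efficacy is unaltered needs evidence that rules out a loss of meaningful size. A difference test without an interval can show that a loss is present, but it does not show how large a loss remains possible when none is detected.

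The sample size does not help here. The choice of 24 patients is justified by each patient acting as his or her own control. Response is measured after cycle 2, before anyone crosses over, so that within-patient gain is not available.

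The question matters within the protocol's own reasoning. Section 1.3.1 describes necrosis as predictive of outcome. Section 1.3.2.1 reports retrospective studies linking high peak methotrexate concentration to better survival, while arguing against peak concentration as the determinant. Table 3 expects the end-of-infusion concentration to be 600 mcM with the 12 h infusion against 1200 mcM with the 4 h infusion. Section 6.2 says the results are meant to justify a randomized cooperative-group trial, so what is said about response will carry forward.

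**Working it through.** **Inputs**
- Six patients per arm (Section 3.2). Two arms are pooled on each side of a factor (Section 6.1.2), so 2 × 6 = 12 versus 12.
- Three per arm among the first 12 patients (Section 3.2), so about 6 versus 6 at the early look.
- Assumed: a Wilcoxon-Mann-Whitney test at two-sided 5%. The plan says only that the analysis is non-parametric.
- The documents give no SD for percent necrosis or log volume ratio, so results are in SD units.

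**1. The plan's own figure for this group size.** For the ototoxicity fallback, Section 6.2 gives 80% power at 1.2 SD with 12 per group, by a two-sided two-sample t test at 0.05. The noncentral t distribution gives 80.2% at 1.2 SD, and the difference detectable with 80% power is 1.197 SD. The figure reproduces, and it applies equally to any 12 versus 12 comparison of a continuous endpoint by t test.

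**2. Power of the rank test, 12 versus 12.** Exact critical value U ≤ 37, actual size 4.5%, normal shift, 40,000 simulated trials per row:

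| True loss | Power | Chance of missing it |
|---|---|---|
| 0.5 SD | 19.5% | 80.5% |
| 0.8 SD | 43% | 57% |
| 1.0 SD | 61% | 39% |
| 1.2 SD | 77% | 23% |
| 1.25 SD | 80% | 20% |

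**3. What a null result would leave open.** The half-width of a 95% CI for a difference in means is t(0.975, 2n−2) × √(2/n) in SD units.
- n = 12: 2.074 × √(2/12) = 2.074 × 0.408 = 0.85 SD.
- n = 6 (early look): 2.228 × √(2/6) = 2.228 × 0.577 = 1.29 SD.
- n = 14 (if all 28 possible enrollees contributed response data): 2.056 × √(2/14) = 2.056 × 0.378 = 0.78 SD.

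**4. In necrosis points, over an assumed range of SD**

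| Assumed SD | Loss detectable with 80% power (t test) | 95% CI half-width |
|---|---|---|
| 15 | 18 | 13 |
| 20 | 24 | 17 |
| 25 | 30 | 21 |
| 30 | 36 | 25 |

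**5. Sensitivity to shape.** Percent necrosis is bounded and probably skewed. With assumed beta distributions (control mean 80–85%, control SD about 15–23 points), rank-test power is 17–32% for a 10-point mean loss and 47–78% for a 20-point mean loss. The conclusion does not depend on normality.

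**6. Fewer specimens.** Section 3.1.6 allows for unresectable primaries, which would have no resected specimen. At 10 versus 10, the t-test detectable difference rises to 1.32 SD.

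**The case against.** Several points on the other side are fair.

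- *No rule turns a non-significant result into a finding of unchanged efficacy.* This stands. A reader might infer from *ensure* plus a difference test that p > 0.05 will be read as proof. No section says so, and Section 2 states the objective only as comparing response. The point is limited to a stated purpose that the analysis cannot deliver.
- *The wording about the anti-tumour effect not being compromised belongs to the early look.* This also stands. Section 6.3, which says how interim response data will be used, relies on the investigators' judgement of clinical significance and plans no test. A reader might want to attach a detectable loss to that look, but there is no planned test for it to describe. Only the imprecision of the estimate, about 1.3 SD either way, is relevant.
- *The small size is admitted.* Partly. Section 6.3 says the sample is too small for a valid stopping rule, and Section 6.2 prints the 1.2 SD figure for hearing. Neither statement is carried to the final response comparison.
- *This is a secondary endpoint in a pilot.* True, and missing power for such an endpoint is not in itself an error. A reader might infer that the pilot could wrongly clear the interventions for general use. The documents do not support that, because the next step named is another randomized trial. This limits the consequence but does not make *ensure* accurate.

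**Conclusion.** The concern holds as a mismatch between claim and design. A loss of up to about 0.8 SD is more likely to be missed than found, 80% power is reached only near 1.25 SD, and an observed difference of zero leaves a loss of about 0.85 SD open. The comparison is a reasonable screen for a large loss and no more than that. A loss of 0.8 SD is not undetectable; it would be found 43% of the time.

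The result rests on 12 evaluable patients per side, a Wilcoxon-Mann-Whitney test at two-sided 5%, and a normal shift in SD units. Skewed necrosis or a few patients more or fewer changes the figures modestly but not the conclusion. The translation into necrosis points depends entirely on the assumed SD. The change should be made: it affects what the trial may conclude about response, although response is secondary and no misuse of a p-value is written into the plan.

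**What to change.** 1. **Section 6.1.2:** for each factor, report the estimated difference in percent necrosis and in log volume ratio with a 95% CI. A Hodges-Lehmann shift would fit the non-parametric approach. Because necrosis is bounded, group medians and individual values are a useful supplement. Stratifying by the other factor is optional. Name the test, its sidedness and its alpha.
2. **Section 6.2:** state that the response comparison is between patients, about 12 versus 12, and reaches 80% power only for losses of about 1.2 SD (t test) to 1.25 SD (rank test).
3. **Synopsis (Study Design) and Section 1.3.7:** replace *ensure* with *estimate* or *screen for a large loss*. Do the same in the Synopsis (Safety Evaluation) and Section 5.4 for the look after 12 resections, noting that at 6 versus 6 the 95% CI half-width is about 1.3 SD.
4. **Permitted conclusion:** say only that losses beyond the confidence limit are excluded.

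The cost is wording plus one extra estimate per comparison, with no added patients, visits or assays. The downside is a less favourable permitted conclusion: the pilot could no longer be described as showing that efficacy is preserved.
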